Carbohydrate mouth rinsing and softball batting performance: a double-blind crossover study

Document Date: Oct 21, 2024

IRB approved date: March 30, 2022

Project summary

Carbohydrate mouth rinsing (CMR) stimulates the central nervous system and improves motor control. However, no studies have examined the effects of CMR on softball batting performance. The purpose of this study was to investigate the effect of CMR on softball batting performance. Fourteen trained collegiate female softball players (age: 20.6 ± 0.9 years; height: 159.5 ± 5.2 cm; body weight: 58.1 ± 6.9 kg) completed two trials in a randomization crossover trail, in which they rinsed their mouths for 20 seconds with 25 ml of either 6.4% maltodextrin (CMR) or placebo (PLA). After rinsing, the grip force, counter-movement jump (CMJ) and batting tests were performed in sequence. The tanner tee was utilised to perform five sets of five balls at a time, with a minimum of 3 minutes rest between sets. The batting test recorded average exit velocity, maximum exit velocity and batting accuracy. The standardized standard deviation (SD) for launch angle represents standardized variability.

Introduction

Many studies have found that pre-exercise carbohydrate supplementation is effective in maintaining high levels of glycogen in muscle and improving endurance performance in activities exceeding an hour in duration (1, 2). However, since Carter et al. (2004) revealed that the use of a carbohydrate mouth rinsing (CMR) still had a significant effect on improving athletic performance over a shorter period of time(3), it has been shown that CMR not only improves endurance performance over a short period of time, but also has a significant effect on high intensity exercise (4), improves resistance training quality (5), muscle strength of the lower limbs (6) and decrease fatigue index during intermittent exercise(7). The potential mechanism may be due to the delaying of fatigue in the central nervous system (8) and may facilitate the activation of the brain regions associated with exercise control(9). It has been proposed that the mechanism of CMR involves the activation of the dorsolateral prefrontal cortex and the ventral striatum (10). The cerebral cortex is integral to cognitive, attentional processing, and motivation (11). The aforementioned phenomena suggest that CMR is not only beneficial for endurance sports but also enhances performance in explosive sports and improves body control during exercise.

In the context of fast pitch softball, enhancing both batting exit velocity and bat control represents a crucial strategy for increase the score and win rate of the game(12). In each swing, it is necessary to combine speed and explosive power. This can be achieved through the use of lower extremity forces, which are employed to transfer weight from the lower to the upper body. The rotation of the torso at a rapid pace also serves to increase the speed of the swing (13). It has been suggested that increase the muscle strength and explosive power of as important factors for improving the exit velocity of the ball for female softball players(14). Previous research has demonstrated the efficacy of CMR in enhancing lower limb strength, explosive power (6), and potentially cognitive function (11). From these perspectives, CMR appears to be a promising approach for enhancing both exit velocity and batting control.

CMR has positive effects on athletic performance and activates areas of the brain related to motor control (9). For softball batting, an increase in batting speed and stable control of the angle of elevation of the bat will improve batting performance and thus increase the team's chances of winning. However, there are no studies that have examined the effect of CMR on batting performance in softball. Therefore, the purpose of this study was to investigate the effect of CMR on the exit velocity and bat control of female softball players.

Methods

Experimental Design

This study was conducted using a single-blind randomized cross-over experimental design, whereby all participants were required to complete two trials. The carbohydrate mouth rinsing trial (CMR) utilised a colourless and odorless water solution, comprising 6.4% maltodextrin. The mineral water was utilised for the placebo trial (PLA). For each rinsing, 25ml of the water solution was used, and the rinsing process was conducted for 20 seconds before the solution was spat back into the original cup. After completing the first experiment, the participant rested for at least 7 days and completed the next experiment.

Participants

A total of 15 female collegiate fast-pitch softball players were recruited for this study. Following the withdrawal of one participant due to personal reasons, the final results of 14 participants (mean age: 20.6 ± 0.9 years; height: 159.5 ± 5.2 cm; mass: 58.1 ± 5.9 kg; mean training age: 6.8 ± 0.8 years) were analysed. The inclusion criteria for this study were: (a) more than 6 years of professional fast-pitch softball training; (b) more than 6 months of continuous training; (c) from at least the top four teams in the country. The exclusion criteria were: (a) non-professionally fast-pitch softball training; (b) lack of regular training in the past 6 months; (c) in the event that the applicant has sustained a sports injury or is currently experiencing epilepsy, hypertension, hyperlipidemia, heart disease, arthritis, osteoporosis, or a brain injury, and has yet to undergo a period of recuperation exceeding three months. All participants signed the consent form after being informed of the procedure and the associated risks prior to the experiment. All tests were completed during non-menstrual periods. The study was approved by the institutional review board of China Medical University Hospital, Taiwan (CMUH110-REC2-253). This study was conducted following the Declaration of Helsinki.

Sample size calculation

We used G*Power software (version 3.1.9.4, Universität Düsseldorf, Germany) (15) to determine the required sample size. The calculation was based on an alpha level of 0.05 and a correlation coefficient of 0.80, which were deemed to be the appropriate levels for the purposes of this study. A previous study demonstrated that CMR enhances lower limb muscle strength, with an effect size of 0.56 (6). The analysis revealed that a sample size of 14 would be sufficient for the purpose of detecting a difference between trials. A sample size of 14 participants should be sufficient to elucidate the statistical discrepancies.

Protocol

The formal examination comprises grip strength assessments, CMJ and batting tests. It is imperative that all participants undergo familiarisation tests on at least two occasions prior to the formal test. Three days prior to the first formal trial, participants were asked to photographically record the contents of all meals as well as the time of consumption. In the next formal experiment, participants were asked to eat exactly the same food at the same consumption time. On the day of the experiment, after a standard lunch at 12:00, arrive at the laboratory at 15:30 for the experiment.

After a five-minute break, the participants were free to warm up dynamically. All warm-up movements and times were recorded and the same movements were used for the next warm-up. After warming up sufficiently, the participant performs the first rinsing, which is followed by a maximum grip strength test with the dominant hand. Perform a total of 3 sessions with a 1-minute break between each session. Following the completion of the grip strength test, the participant was permitted a three-minute period of rest. Subsequently, they rinsed their mouth and proceeded to undertake the CMJ test on 3 occasions, with a one-minute interval between each attempt. In previous studies, a positive correlation has been identified between grip strength, jump height and the exit velocity of a ball in baseball players (16). After completing these tests, participants underwent a 5-minute dynamic warm-up of batting. The tanner tee was utilised to perform five sets of five balls at a time, with a minimum of 3 minutes rest between sets. Participants rinsed their mouths before each batting tests.

Outcome measure

In the grip strength test, the participant assumed a standing position with a standardised hand-held grip dynamometer (Smedlay's Hand Grip Dynamometer TTM, Japan) and adjusted the grip to the second knuckle, with the arm at an approximately 10° angle to the trunk. The participant was instructed to position the grip at an angle of between 0 and 15 degrees to the trunk and to press the grip continuously for approximately three seconds with maximum strength, maintaining stability of the trunk throughout the procedure. The procedure was repeated three times, with a one-minute rest interval between each repetition, and the resulting data were averaged (17).

A countermovement jump test was conducted utilising a jumping mat (Fusion Sport, Coopers Plains, QLD, Australia) to evaluate the participants. The participants were instructed to maintain a static standing position on the jumping mat with their arms

folded at the waist. Subsequently, the subjects were given instructions by the instructor and then maintained a position with their arms akimbo, before rapidly squatting to approximately 90° of knee flexion before performing a maximal vertical jump. The hip and knee joints were maintained in an extended position throughout the jump. Trials in which the knee was flexed to an angle of less than 90 degrees or in which the foot made contact with the ground were excluded from the analysis. Each participant completed three trials, with a one-minute interval between each trial. The mean value was then calculated (18).

In the batting test, the tanner tee is used. Place the tanner tee on the front edge of the center of the plate and adjust the height of the tanner tee to approximately the navel of the test participant. Set the batting target at a 10-degree angle, 10 metres in front of the plate, and ask the batter to hit each ball to the target, 5 swings per set, for a total of 5 sets. Hitting data is collected using Rapsodo Hitting 2.0 (Rapsodo Bassball System, Rapsodo Inc, Fishers, IN). This instrument has been employed in previous studies and has demonstrated sufficient reliability for the measurement of exit velocity and launch angle (19). Batting tests evaluate exit speed of the softball and launch angle, and calculated the standard deviation of launch angle, which is used as an indicator of batting consistency(19).

Statistical analysis

The data from this study were presented as mean \pm standard deviation and underwent analysis using the statistical software package SPSS 23.0. The normality of the data was evaluated through the utilisation of the Shapiro–Wilk test. The data are presented according to a normal distribution, and a parametric methodology can thus be applied to statistical analysis. Paired samples t-tests were employed to ascertain the statistical significance of the observed differences in hand grip strength, countermovement jump, average batting exit velocity, maximum batting exit velocity and the SD of the launch angle. The significance level was set at $\alpha<0.05$.

Reference

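### No primary outcome is named among five tests at 0.05; if any one of the three batting tests may count, a false finding in favour of CMR has a chance of about 5–7% instead of 2.5%

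*Protocol*

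**What the plan says.** The Statistical analysis section lists its tests in one sentence: "Paired samples t-tests were employed to ascertain the statistical significance of the observed differences in hand grip strength, countermovement jump, average batting exit velocity", continuing with "maximum batting exit velocity and the SD of the launch angle". That makes five paired t-tests under a single significance level of 0.05. No order or rank is given, and sidedness is not stated.

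The purpose is worded twice. The Project summary has "The purpose of this study was to investigate the effect of CMR on softball batting performance". The end of the Introduction is narrower: "the purpose of this study was to investigate the effect of CMR on the exit velocity and bat control of female softball players".

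The batting outcomes are also labelled in two ways. The Project summary says "The batting test recorded average exit velocity, maximum exit velocity and batting accuracy", followed directly by "The standardized standard deviation (SD) for launch angle represents standardized variability". The Outcome measure section sets up a target ("ask the batter to hit each ball to the target") but derives only exit speed, launch angle and one variability measure: "calculated the standard deviation of launch angle, which is used as an indicator of batting consistency". No separate accuracy score is defined or tested.

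Grip strength and jump height are introduced in the Protocol subsection of the Methods through their reported correlation with exit velocity in baseball players. The Participants section shows that the 14 players' results have already been analysed.

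**The concern.** Three batting p-values bear on a question about batting, and nothing says which one answers it. The broader purpose leaves any of them open to be read as the answer. The narrower one points to two constructs covered by three tests. The sample size calculation does not settle the matter, because its effect size of 0.56 comes from lower-limb muscle strength, which is not a batting measure.

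If the result that happens to be significant becomes the headline, the error rate of the claim is that of the set of tests and not of one test. The list also does not mark grip strength and countermovement jump (CMJ) as supporting measures, so a significant result there could be reported alongside the batting results as if it carried the same weight.

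**Working it through.** **Inputs from the protocol.** n = 14 pairs (13 degrees of freedom); 0.05 per test; three batting tests (average exit velocity, maximum exit velocity, SD of launch angle); effect size 0.56 and correlation 0.80 from the Sample size calculation.

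**Assumptions.** Two-sided tests; no true difference on any outcome; correlations between the outcome differences of 0 to 0.8 (up to 0.9 for the two velocity measures). The protocol gives none of these. Signs are set so that positive favours CMR, so a smaller SD of launch angle counts as favourable.

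**Step 1: the plan's own figure.** Read 0.56 as a raw standardised difference and convert it with r = 0.80: dz = 0.56/√(2 × (1 − 0.80)) = 0.885. The noncentral t then gives 13 participants for 80% power, 14 for 85% and 16 for 90%, with 86.4% power at n = 14. The stated 14 is reproduced on that reading. If 0.56 is already dz, 80% power needs 28 and power at n = 14 is 49.2%. The protocol does not say which is meant.

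**Step 2: one test.** 5% in either direction, 2.5% in favour of CMR.

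**Step 3: any one of the three batting tests.** If the tests are independent:
- either direction: 1 − 0.95³ = 0.143
- in favour of CMR: 1 − 0.975³ = 0.073

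Whatever the correlations, the ceilings are 3 × 0.05 = 0.15 and 3 × 0.025 = 0.075. Simulated paired t-tests on correlated normal differences (n = 14, 300,000 replicates) give the correlated cases:

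| Correlation assumed | Either direction | In favour of CMR |
|---|---|---|
| All three at 0.8 | 10.1% | 5.0% |
| Only average and maximum velocity at 0.8 | 12.6% | 6.4% |
| Independent | 14.3% | 7.3% |

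Average and maximum exit velocity come from the same 25 swings (five sets of five), so a high correlation between those two is plausible.

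**Step 4: exit velocity and bat control as separate questions.** Bat control has one test, so 5% and 2.5%. Exit velocity has two:

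| Correlation assumed | Either direction | In favour of CMR |
|---|---|---|
| 0.9 | 7.2% | 3.6% |
| 0.8 | 7.9% | 3.9% |
| Independent: 1 − 0.95², 1 − 0.975² | 9.75% | 4.9% |

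**Step 5: the effect of Holm over three tests.** The chance of any false rejection becomes about 4.9% (2.5% in favour) if independent and 3.7% (1.9%) with all correlations at 0.8.

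**Step 6: the price in power.** The first Holm step is 0.05/3 = 0.0167. Power of a single test at n = 14 falls from 86.4% to 70.8% with dz = 0.885, or from 49.2% to 30.0% with dz = 0.56. For 80% power at that level, n would be 17 or 37, against 13 or 28 at 0.05.

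**The case against.** The strongest reply is that the protocol states no rule under which any one result suffices. The Introduction gives the specific purpose, and on that reading bat control has a single test and no inflation. This stands, and it makes the 5–7% conditional. It does not remove the point for exit velocity, where two tests remain and neither is preferred.

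A second reply is that grip strength and CMJ are already supporting measures by context, since both purposes are about batting. This is largely fair. The analysis section simply does not say so.

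A third is that a statistical analysis plan may hold a multiplicity procedure. It may, so the absence of an adjustment method is not the finding. The finding is what this document fixes: five tests at 0.05 with no outcome singled out.

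Three stronger readings are tempting, and the document does not support them:
- **A 10–14% risk of a false claim of benefit.** That range includes results in favour of placebo. The figure for benefit is 5–7%, and its comparator is 2.5%.
- **A rate over all five outcomes.** This would be about 13–23% in either direction (correlations from 0.8 to 0). The stated purposes concern batting, so a grip or jump result does not answer them.
- **A fourth batting outcome.** The Project summary's mention of batting accuracy might suggest one. The next sentence there turns to the SD of launch angle, and the Methods define and test only that SD. Loose naming of one outcome is the simpler explanation, so this is a matter of wording.

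**Conclusion.** The point holds in a limited form. The protocol tests five outcomes at 0.05 and selects no primary outcome through its purposes, its sample size basis or its analysis text. If any one of the three batting tests is accepted as showing an effect, the chance of a false finding in favour of CMR is two to three times that of a single test: 5.0–7.3% against 2.5%. If exit velocity and bat control are kept as two questions, the excess is confined to exit velocity, at 3.6–4.9% against 2.5%.

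The sizes rest on two-sided testing, no true effects and assumed correlations. The absence of a named primary outcome and the mismatch in batting labels rest on the text alone. This should be fixed, but it does not by itself invalidate the trial.

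**What to change.** 1. If a single primary batting outcome was documented before the data were seen, name it and test it at 0.05.
2. If not, state that none was prespecified. Report Holm-adjusted p-values over the three batting outcomes, labelled post hoc.
3. Either way, give the mean difference and 95% confidence interval for every outcome. Present grip strength and CMJ as supporting measures that do not by themselves support a batting claim.
4. Align the Project summary's batting accuracy and standardized SD with the SD of launch angle in the Methods, and say whether that SD is raw or standardized. If accuracy is in fact a separate outcome, define it and add it to the Holm family.

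**Cost.** No new data: a reconciled outcome list, adjusted p-values, intervals and a sentence of disclosure. Power for a single batting test at the first Holm step falls from about 86% to 71%, or from about 49% to 30%, depending on how 0.56 is read; that effect size is borrowed from lower-limb strength and may not carry over to batting. The loss is smaller when any one rejection is enough. With a true dz of 0.885 on all three outcomes, the chance of at least one Holm rejection is about 84% with all correlations at 0.8, and 94% with only the two velocity measures at 0.8 (simulated, n = 14). Holm chosen after the data were analysed cannot restore prospective error control, so the disclosure is the firm part of the remedy.

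### The randomised two-period crossover is analysed by plain paired t-tests with no period term, so any shift between sessions is counted as random error and costs power

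*Protocol*

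**What the plan says.** Under Experimental Design, the protocol describes a "single-blind randomized cross-over experimental design, whereby all participants were required to complete two trials". The spacing is given there too: "After completing the first experiment, the participant rested for at least 7 days and completed the next experiment".

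Under Statistical analysis, the same method is fixed for grip strength, countermovement jump, average exit velocity, maximum exit velocity and the SD of launch angle: "Paired samples t-tests were employed to ascertain the statistical significance of the observed differences". Neither that section nor any other mentions period, sequence or order of treatment.

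Two further places bear on the point. The Protocol section tries to limit practice effects: "It is imperative that all participants undergo familiarisation tests on at least two occasions prior to the formal test". It also has meals and warm-up repeated in the second session. The Participants section says that 15 players were recruited and accounts for the analysed set as follows: "Following the withdrawal of one participant due to personal reasons, the final results of 14 participants". It does not say how those 14 divide between carbohydrate first and placebo first.

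**The concern.** In a two-period crossover, each player's carbohydrate-minus-placebo difference contains the treatment effect and any general change from session 1 to session 2, such as practice, form or training state. That change is subtracted in players who had carbohydrate first and added in players who had placebo first. A paired t-test ignores which order a player had. It therefore sees two groups of differences pulled apart by twice the shift and counts the gap as noise.

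Two things are at stake. With equal numbers per order, the shift cancels in the mean but inflates the SD, so the confidence interval is too wide and power is lost in a trial of only 14 players. With unequal numbers, part of the shift also remains in the treatment estimate. Because order was randomised, a period term can separate the shift from treatment; the stated analysis does not use it.

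The protocol itself fixes the paired t-test, so this is not a detail left to a later plan.

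**Working it through.** **Inputs from the protocol.** Effect size 0.56, n = 14, and, under Sample size calculation: "The calculation was based on an alpha level of 0.05 and a correlation coefficient of 0.80". Two-sided testing is assumed, since sidedness is not stated.

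**Reproducing the planned sample size.** Reading 0.56 as a between-condition effect, the standardised paired difference is dz = 0.56/√(2 × (1 − 0.80)) = 0.56/√0.4 = 0.885. A paired t-test at two-sided 0.05 then needs 13 players for 80% power and 14 for 85%. Power at n = 14 is 86.4%. The protocol's 14 is therefore reproduced at 85% power, although it states no target power. If 0.56 were dz itself, 80% power would need 28 players.

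**Model.** Let π be the session-2-minus-session-1 shift in units of the SD of the paired difference. The documents do not give π, so the values below are assumptions. One unit of π equals √0.4 = 0.632 outcome SD. Each player's difference is D = dz − π (carbohydrate first) or dz + π (placebo first), plus error with SD 1.

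- *Paired t-test, 13 df.* With n1 players carbohydrate-first and n2 placebo-first, the mean of D is dz − π(n1 − n2)/14. The sum of squares is noncentral chi-square on 13 df, with noncentrality 14π²(1 − ((n1 − n2)/14)²). At 7/7 the mean is unbiased and the expected variance is 1 + 14π²/13. At π = 0.5 that is 1.27.
- *Period-adjusted test, 12 df.* SE = ½√(1/n1 + 1/n2). At 7/7 this is 0.267 = 1/√14, free of π.

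**Results at 7/7, two-sided 0.05**

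| π | Shift in outcome SD | Paired power | Adjusted power | Paired power if dz = 0.56 | Paired type I error | CI width, paired/adjusted |
|---|---|---|---|---|---|---|
| 0 | 0 | 86.4% | 86.0% | 49.2% | 5.0% | 0.99 |
| 0.16 | 0.10 | 85.8% | 86.0% | 48.1% | 4.7% | 1.01 |
| 0.3 | 0.19 | 84.2% | 86.0% | 45.6% | 4.1% | 1.04 |
| 0.5 | 0.32 | 79.9% | 86.0% | 39.6% | 3.0% | 1.12 |
| 1.0 | 0.63 | 58.6% | 86.0% | 19.4% | 0.6% | 1.43 |

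With dz = 0.56, adjusted power is 48.7% at every π. With dz = 0.885, the period term starts to gain power at π of about 0.14 (0.14 × 0.632 = 0.09 outcome SD). Simulation with 200,000 or more replicates per setting agreed with the power and type I error figures.

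**Unequal orders.** The bias is π × 2/14 = 0.14π in size at 8/6 and π × 4/14 = 0.29π at 9/5. Power can move either way:

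- At 8/6 with eight carbohydrate-first and π = 0.5, paired power is 72.6%, against 85.3% adjusted.
- With six carbohydrate-first it is 86.1%, but the apparent gain is bias towards carbohydrate.
- Paired type I error at 8/6 is 4.4%, 3.5% and 1.3% at π = 0.3, 0.5 and 1.0. At 9/5 it lies between 4.3% and 5.2%.

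**The case against.** The strongest reply is that the harm depends entirely on a shift that the documents neither report nor imply, and the design works against one. It has experienced players, at least two familiarisation tests, repeated meals and warm-ups, a fixed lunch and arrival time, and at least 7 days between sessions. The large losses come from large assumed shifts: π = 1.0 is 0.63 outcome SD, more than the 0.56 effect the trial was sized on. Up to π = 0.3 the loss is under 2 points (86.0 − 84.2 = 1.8), and below about 0.14 the period term is slightly worse. At 7/7 the paired t-test is valid, and nothing shows that the split was not 7/7.

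Most of this stands as a limit on weight. No inflation of false positives is at issue, and a shift as large as 1.0 has no support in the documents. A fixed period term also removes only the shift common to all players; changes particular to a player stay in the error under either analysis.

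It does not rescue the choice of test. Familiarisation and standardisation reduce a shift without showing that it is zero. As its size is unknown, the choice should be judged on the trade-off. At 7/7 the period term costs at most half a point, while leaving it out costs about 6 points at π = 0.5 (86.0 − 79.9). The split also cannot be checked from what is reported. Fifteen recruits cannot divide equally; if they were allocated 8/7 (an assumption), one withdrawal leaves either 7/7 or 8/6.

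**Conclusion.** The concern holds. It is a loss of efficiency, with a possible small bias if the orders are unequal; it does not threaten the validity of the paired t-test at 7/7.

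Under the protocol's own planning figures and a 7/7 split, the loss against a period-adjusted test is negligible for shifts below about 0.2 SD of the paired difference. It is 1.8 points at 0.3, about 6 at 0.5 and about 27 at 1.0. These sizes rest on two-sided testing, on reading 0.56 as a between-condition effect, and on assumed values of the shift. Reading 0.56 as dz lowers all the power figures but leaves the pattern unchanged.

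The change is worth making because it is cheap and uses the order the trial already randomised.

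**What to change.** Analyse each outcome with treatment and period as fixed effects and player as a random effect. Equivalently, for players with both trials, take each player's session-1-minus-session-2 difference, compare the two orders by a two-sample t-test, and halve the estimated difference. Report the number of analysed players in each order.

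The protocol describes the 14 results as already analysed. The period-adjusted result should therefore be shown beside the paired t-test and labelled as added afterwards.

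The cost is one degree of freedom (13 to 12). With no shift, power goes from 86.44% to 85.97% at 7/7, to 85.3% at 8/6 and to 83.0% at 9/5: losses of about 0.5, 1.2 and 3.5 points from unrounded values. No new data are needed, and the analysis runs in SPSS.
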